4.1. Overall Design

Study KFAJ is a multicenter, randomized, double-blind, placebo-controlled, parallel-group Phase 2 study to evaluate the efficacy and safety of LY3471851 in adult study participants with at least moderately active SLE. The study has 3 required study periods and an optional prescreening period. A schematic of the study design is presented in Section 1.2.

Optional prescreening period

Study participants must have positive antinuclear, CCI [REDACTED] at Visit 1 to be eligible for randomization at Visit 2. The optional prescreening visit (Visit 601) is intended for those investigators who opt for central laboratory assessment of the prospective participant's antinuclear antibodies (ANA), CCI [REDACTED] status before full screening activities are initiated.

If opted for, the prescreening determination of ANA, CCI [REDACTED] status will be described in an appropriate informed consent form (ICF). Informed consent for the prescreening activities will be obtained, a participant identification number will be assigned, and samples for specified laboratory tests will be obtained. The optional prescreening visit can be repeated 2 times (no more) per participant, with a minimum of 4 weeks between visits. Repeated visits in the prescreening visit will not require re-consenting or assignment of a new participant identification number.

Note: If the optional prescreening is opted for, central laboratory testing for ANA, CCI [REDACTED] is still required as part of the screening procedures conducted at Visit 1. Participants with negative results at Visit 1 will not be eligible for enrollment, despite positive values in prescreening.

Screening period

The required screening period begins with Visit 1, which occurs within 5 weeks before the planned randomization visit. If the participant had an optional prescreening visit, an assessment of ANA, CCI [REDACTED] will be repeated at Visit 1 for confirmation of study eligibility. The main Study KFAJ ICF will be signed before Visit 1 procedures are performed. A participant identification number will be assigned at Visit 1, if one was not assigned at Visit 601. Participant eligibility will be reviewed and confirmed by an eligibility review committee prior to randomization.

Participants found to be eligible according to all of the study entry criteria will be randomly assigned in a 1:1:1:1 ratio to receive one of the following study interventions:

- CCI [REDACTED] LY3471851 every 2 weeks (Q2W)
- CCI [REDACTED] LY3471851 Q2W
- CCI [REDACTED] LY3471851 Q2W, or
- placebo Q2W.

CCI

Study interventions will be administered via subcutaneous injection (SC).

Double-blind treatment period

Randomized participants will begin the double-blind, placebo-controlled, 24-week treatment period at Visit 2. Participants will receive the first dose of the assigned study intervention at that visit and will continue to receive doses through the last scheduled dosing visit specified in the Schedule of Activities (SoA, Section 1.3). Participants will maintain their usual standard-of-care medication regimen for SLE and for other diseases throughout the study, unless these medication regimens are specifically excluded by the study entry criteria. Safety and efficacy assessments and laboratory sample collections will be performed as specified in the SoA.

Follow-up period

All participants will have a post-treatment follow-up visit (Visit 801) for safety assessments. Randomized participants who were positive for hepatitis B core antigen (anti-HBc) at screening will have one additional post-treatment follow-up visit (Visit 802).

Early discontinuation

Participants who permanently discontinue the study drug early or withdraw from the study (Section 7) will undergo early termination procedures, including an early termination visit (ETV) and the post-treatment follow-up visits specified in the SOA.

4.2. Scientific Rationale for Study Design

SLEDAI-4 response as the primary endpoint

The primary endpoint is the proportion of participants who achieve a SLEDAI-4 response at Week 24 (Section 8.1.1). The selection of SLEDAI-4 for the primary endpoint measure was based on analyses from 2 recent SLE Phase 3 studies involving more than 2200 patients in a similar patient population (Isenberg et al. 2016; Merrill et al. 2016). The purpose of those analyses was to characterize the clinical signs and symptoms most responsible for achieving responder status with Systemic Lupus Erythematosus Responder Index-5 (SRI-5), and then to use this information to design a more efficient study with clinically relevant endpoints (Kalunian et al. 2018). The primary endpoint of those 2 recent studies required a 5-point reduction in SLEDAI with no worsening in British Isles Lupus Assessment Group (BILAG) score or Physician's Global Assessment of Disease Activity (PGA). The analyses found that fewer than 1% of the study participants failed on SRI-5 due to BILAG or PGA worsening after achieving a ≥ 5 -point reduction in SLEDAI. Also, in the belimumab phase 3 SLE trials (as reported in Arthritis Advisory Committee meeting briefing document 2010), the proportion of patients with a ≥ 4 -point reduction in SLEDAI that failed to achieve a Systemic Lupus Erythematosus Responder Index-4 (SRI-4) due to worsening of the BILAG or PGA ranged from 0.3% to 2.2% (Kalunian et al. 2018). These data provide a rationale to focus on SLEDAI as the primary driver of clinical response. A 4-point reduction in SLEDAI is considered clinically meaningful and serves as the basis for the primary endpoint of SLEDAI-4 (Gladman et al. 2000).

Appropriateness of study population

Patients with at least moderately active SLE are an appropriate study population for a novel investigational product with immunomodulating properties. The study entry criteria will enable enrollment of patients who are representative of the general population of patients with at least moderately active SLE as defined by Systemic Lupus Erythematosus Disease Activity Index (SLEDAI) ≥ 6 during screening and ≥ 4 for clinical features at randomization before administration of study drug. This SLEDAI cutoff has been used in other Phase 2 studies of SLE (van Vollenhoven et al. 2018; Wallace et al. 2018).

Choice of control and number of treatment groups

A double-blind, placebo-controlled design limits bias for both participant assessments and investigator assessments and enables a clearer interpretation of the effects of active drug. The selection of placebo as a comparator for this study is warranted because there are few approved therapies for SLE and because study participants will be permitted to receive concomitant standard-of-care therapies. The multiple active dose levels will allow for an evaluation of safety and efficacy across a broad dose range and so provide information to guide dose selection for future studies.

Duration of treatment period and post-treatment follow-up

Evaluation of measures of efficacy at the Week 24 time point is consistent with the duration of treatment at the primary endpoint for proof-of-concept studies of other interventions for SLE (Furie et al. 2017; van Vollenhoven et al. 2018; Wallace et al. 2018).

In longer studies, SLE efficacy outcomes at Week 24 are similar to those observed at Week 52, which is the time point typically used for registration studies (Furie et al. 2011; Navarra et al. 2011; Isenberg et al. 2016; Merrill et al. 2016). Clinically meaningful effects were observed earlier than 24 weeks in open-label SLE studies of low-dose IL-2 formulations (He et al. 2016 [rhIL-2^{Ser125}]; Rosenzweig et al. 2019 [aldesleukin and ILT-101]), which are hypothesized to work through a mechanism of action similar to that of LY3471851.

A post-treatment study visit will occur at Week 30, which is 8 weeks after the last dose of investigational product and corresponds to approximately 5 half-lives.

Optional prescreening period

An optional prescreening period was included in the study design to reduce the number of screen failures. In previous studies of SLE, the absence of autoantibodies, as assessed by the central laboratory during the screening period, has been a major reason for screening failures.

4.2.1. Participant Input into Design

The sponsor involved patients in the design of this study by engaging patients in simulations and other face-to-face or virtual collaborative events for related SLE trials. The insights gained from these events were used to ensure that this study design is supportive of the well-being of the study participants and that the study procedures can be implemented effectively at the investigative sites.

4.3. Justification for Dose

Dose selection

The doses were selected based on evaluation of clinical safety, pharmacokinetic (PK), and pharmacodynamic (PD) data from a single-ascending dose study in healthy volunteers (SAD, Study 16-358-01), a multiple-ascending dose study in SLE patients (MAD, Study 17-358-02), and on nonclinical toxicology data.

The available clinical safety data, CCI [REDACTED] supports continued development over a longer time course in Phase 2, given the safety monitoring planned for individual participants and the planned safety data reviews (Section 8.2).

The lowest dose CCI [REDACTED] is predicted to achieve exposures that are within the range of exposures achieved with the CCI [REDACTED] doses previously administered in the SAD and MAD studies. These doses were associated with pharmacological effects. For example, up to a CCI [REDACTED] from baseline was observed in the percentage of CD25^{bright} Tregs, with a similar fold change in absolute numbers of CD25^{bright} Tregs reported.

The highest dose CCI [REDACTED] is predicted to achieve exposures that are similar to a dose of CCI [REDACTED] the highest dose tested in the MAD study. This dose was associated with pharmacological effects; increases in CD25^{bright} Tregs and total Tregs were observed at this dose. An approximate CCI [REDACTED] increase from baseline was observed in the absolute numbers of CD25^{bright} Tregs reported, which did not return to baseline between doses. The numbers of NK cells were highly variable across patients, with an increase in the absolute numbers of NK cells observed CCI [REDACTED] CCI [REDACTED]

[REDACTED]

An intermediate dose CCI [REDACTED] will also be evaluated. This dose is predicted to achieve exposures that are similar to a dose CCI [REDACTED] tested in both the SAD and the MAD studies. In the MAD study, the CCI [REDACTED] dose was associated with increases in CD25^{bright} Tregs and total Tregs; an approximate CCI [REDACTED] increase from baseline was observed in the absolute numbers of CD25^{bright} Tregs reported after each of the three doses, which did not return to baseline between doses. There was minimal effect on absolute numbers of NK cells at this dose level.

CCI [REDACTED]

[REDACTED]

[REDACTED]

[REDACTED]

[REDACTED]

[REDACTED]

4.4. End-of-Study Definition

A participant is considered to have completed the study if he or she has completed all required periods of the study, including the last visit or the last scheduled procedure shown in the SoA (Section 1.3).

The “end of the study” is defined as the date of the last visit or last scheduled procedure shown in the SoA for the last participant in the study globally.

5. Study Population

Prospective approval of protocol deviations to recruitment and enrollment criteria, also known as protocol waivers or exemptions, is not permitted.

All screening evaluations must be completed and reviewed to confirm that potential participants meet all eligibility criteria. Participant eligibility will be reviewed and confirmed by an eligibility review committee prior to randomization.

The investigator will maintain a screening log to record details of all participants screened and to confirm eligibility or record reasons for screening failure, as applicable.

For rescreening and retesting activities within the screening period, see Section 5.4.

5.1. Inclusion Criteria

Patients will be included in the study only if all of the following inclusion criteria are met:

Informed consent

- [1] Are capable of giving signed informed consent as described in Appendix 10.1, which includes compliance with the requirements and restrictions listed in the ICF and in this protocol.

Participant characteristics

- [2] Are male or female patients from 18 to 65 years of age (inclusive), at the time of screening (Visit 1).

Note: Contraceptive use by men or women should be consistent with local regulations regarding the methods of contraception for those participating in clinical studies. For the contraception requirements of this protocol, see Appendix 10.4.

SLE-related inclusion criteria

- [3] Have received a clinical diagnosis of SLE at least 24 weeks before the screening visit (Visit 1).
- [4] Have documentation of having met at least 4 of the 11 Revised Criteria for Classification of Systemic Lupus Erythematosus according to the 1997 Update of the 1982 ACR (Tan et al. 1982; Hochberg 1997) before randomization.
- [5] Have a positive ANA (titer $\geq 1:80$) and/or a positive CCI antibody test at screening (Visit 1) as assessed by the central laboratory.

Note: This criterion must be assessed on the samples collected at Visit 1, not the prescreening samples collected at Visit 601. For repeat testing for ANA, CCI during the screening period, see Section 5.4.1.

- [6] Have a SLEDAI-2K score ≥ 6 at screening (Visit 1) and clinical SLEDAI-2K score ≥ 4 at randomization (Visit 2).
- [7] Have active arthritis and/or active rash as defined by the SLEDAI-2K at screening and at randomization.

5.2. Exclusion Criteria

Patients will be excluded from the study if any one of the following criteria are met:

Corticosteroid use

- [8] Are currently receiving oral corticosteroids at doses >20 mg per day of prednisone (or equivalent) or have adjusted the dosage of corticosteroids within 2 weeks before randomization (Visit 2).
- [9] Have received topical corticosteroids, other than stable doses of Class VI (mild, such as desonide) or Class VII (least potent, such as hydrocortisone), within 8 weeks before randomization (Visit 2).
- [10] Have received parenteral (that is, intravenous or intramuscular) corticosteroids within 12 weeks before randomization (Visit 2) or are expected to require parenteral corticosteroids during the study.

Other prior or concomitant therapy

- [11] Have started treatment with or adjusted the dosage of NSAIDs intended for treatment of signs and symptoms of SLE within 2 weeks before randomization (Visit 2).
- [12] Have started treatment with or adjusted the dosage of an antimalarial (such as hydroxychloroquine, chloroquine, or quinacrine) within 12 weeks before randomization (Visit 2); or have received more than a single antimalarial within 12 weeks before randomization (Visit 2).
- [13] Have started treatment with or adjusted the dosage of an immunosuppressant (such as methotrexate, azathioprine, mycophenolate mofetil, or mizoribine,) within 12 weeks before randomization (Visit 2); or have received more than a single immunosuppressant within 12 weeks before randomization (Visit 2).
- [14] Have received an oral calcineurin inhibitor, such as cyclosporine, tacrolimus, sirolimus, or voclosporin, within 12 weeks before randomization (Visit 2).
- [15] Have received an oral Janus kinase (JAK) inhibitor, including but not limited to baricitinib, tofacitinib, and upacitinib, within 12 weeks before randomization (Visit 2).
- [16] Have received cyclophosphamide (or any other cytotoxic agent) within 12 weeks before randomization (Visit 2).
- [17] Have received biologic therapies in the specified number of weeks before screening:
 - [17a] rituximab or ustekinumab within 24 weeks before randomization (Visit 2),
 - [17b] other biologic therapies including, but not limited to, anticytokine or receptor blocker (etanercept, infliximab, certolizumab, adalimumab, golimumab, tocilizumab, anakinra, ixekizumab, secukinumab, belimumab, abatacept) within 12 weeks before randomization (Visit 2).
- [18] Have received intravenous Ig within 24 weeks before randomization (Visit 2).
- [19] Have received plasmapheresis within 12 weeks before randomization (Visit 2).

- [20] Have received any live vaccine (that is, live attenuated) within 12 weeks of screening (Visit 1), or intend to receive a live vaccine during the study, or plan to receive such vaccine within 8 weeks of completing treatment in this study.
- [21] Have received a Bacillus Calmette-Guerin (BCG) vaccination or treatment within 12 months of screening (Visit 1) or intend to have vaccination with BCG during the course of the study, or plan to receive such vaccination within 8 weeks of completing treatment in this study.
- [22] Have participated within the last 30 days in a clinical study involving an investigational product. If the previous investigational product has a long half-life, at least 5 half-lives or 30 days (whichever is longer) should have passed before the randomization visit (Visit 2) of Study KFAJ.
- [23] Have received treatment with aldesleukin or other IL-2-related treatment.

Current or historical infections

- [24] Have a current or recent acute, active infection. For at least 30 days prior to screening (Visit 1) and up to the time of randomization (Visit 2), participants must have no symptoms or signs of confirmed or suspected infection, and must have completed any appropriate anti-infective treatment.

Note: Participants with an upper respiratory infection or a vaginal/oral candida infection being treated only symptomatically and not requiring systemic anti-infectives may be considered for enrollment if other eligibility criteria are met. Other uncomplicated local infections should be discussed with the sponsor's medical monitor.

- [25] Have had, within 12 weeks before randomization (Visit 2), any of the following types of infection:
- Serious (requiring hospitalization, and/or intravenous or equivalent oral antibiotic treatment),
 - Opportunistic (as defined in Winthrop et al. 2015),
Note: Herpes zoster is considered active and ongoing until all vesicles are dry and crusted over,
 - Chronic (duration of symptoms, signs, and/or treatment of 6 weeks or longer),
 - Recurring (including, but not limited to, herpes simplex, herpes zoster, recurring cellulitis, chronic osteomyelitis).

Note: Participants with only recurrent, mild and uncomplicated orolabial and/or genital herpes may be considered for enrollment if discussed with the sponsor's designated medical monitor and if other eligibility criteria are met.

- [26] Have human immunodeficiency virus (HIV) infection.
- [27] Have a current infection with hepatitis B virus (HBV DNA) (that is, positive for hepatitis B surface antigen [HBsAg] and/or PCR positive for HBV DNA).
- [28] Have a current infection with hepatitis C virus (that is, positive for HCV RNA).
- [29] Have current or past history of active tuberculosis (TB) (see Section 8.2.6).

- [30] Have or have had latent TB infection (LTBI) that has not been treated with a complete course of appropriate therapy as defined by the World Health Organization and/or the United States Centers for Disease Control and Prevention, unless such treatment is underway (see Section 8.2.6).

Other current or historical medical conditions

- [31] Have severe active lupus nephritis defined clinically and/or by urine protein/creatinine ratio >300 mg/mmol (as an estimate of approximate proteinuria >3 g/day) or active urinary sediment with red blood cell cast(s), or histological evidence of lupus nephritis (Class III, IV, V, or VI according to the International Society of Nephrology classification criteria) within 12 weeks before randomization (Visit 2).

Note: For laboratory retesting related to lupus nephritis, see Section 5.4.1.

- [32] Have active severe central nervous system lupus including aseptic meningitis, cerebral vasculitis, demyelinating syndrome, myelopathy, acute confusional state, psychosis, acute inflammatory demyelinating polyradiculoneuropathy, cranial neuropathy, plexopathy, status epilepticus, or cerebellar ataxia within 24 weeks before randomization (Visit 2).
- [33] Have active fibromyalgia that, in the investigator's opinion, would make it difficult to appropriately assess SLE activity for the purposes of this study.
- [34] Have been treated for or had an active occurrence of a systemic inflammatory condition other than SLE, such as, but not limited to, rheumatoid arthritis, juvenile chronic arthritis, spondyloarthropathy, Crohn's disease, ulcerative colitis, or psoriatic arthritis in the 12 weeks before randomization (Visit 2).

Note: Participants with secondary Sjögren's syndrome are not excluded.

- [35] Have experienced a thrombotic event within 24 weeks before randomization or are on anticoagulants and in the opinion of the investigator are not well-controlled regarding management of hypercoagulable risk.
- [36] Have experienced any of the following within 12 months before screening: myocardial infarction, unstable ischemic heart disease, stroke, or New York Heart Association Stage IV heart failure.
- [37] Have a history of clinically significant or uncontrolled cardiovascular disease (for example, hypertension, angina, congestive heart failure); endocrine disorder (for example, diabetes, thyroid dysfunction); or respiratory, hepatic, renal, gastrointestinal, hematologic, or neuropsychiatric disorder; or any other serious and/or unstable illness that in the opinion of the investigator, could constitute an unacceptable risk to the participant when taking an investigational product or could interfere with the interpretation of study data.
- [38] Are, in the judgment of the investigator, actively suicidal and therefore deemed to be at significant risk for suicide.
- [39] Have answered "yes" to either Question 4 or Question 5 on the "Suicidal Ideation" portion of the Columbia-Suicide Severity Rating Scale (C-SSRS) **or** have answered "yes" to any of the suicide-related behaviors on the "suicidal behavior" portion of the C-SSRS,

and the ideation or behavior occurred within 4 weeks prior to randomization (Visit 2).

- [40] Have a history of lymphoproliferative disease; or have signs or symptoms suggestive of possible lymphoproliferative disease, including lymphadenopathy or splenomegaly (other than primarily because of SLE); or have active primary or recurrent malignant disease; or have been in remission from clinically significant malignancy for <5 years.

Exceptions:

- Participants with cervical carcinoma in situ that has been resected with no evidence of recurrence or metastatic disease for at least 3 years may participate in the study if other study entry are met.
 - Participants with basal cell or squamous epithelial skin cancers that have been completely resected with no evidence of recurrence for at least 3 years may participate in the study if other study entry criteria are met.
- [41] Have had any major surgery within 12 weeks before randomization (Visit 2) or will require major surgery during the study that, in the opinion of the investigator in consultation with Lilly or its designee, would pose an unacceptable risk to the participant.
- [42] Have a known allergy to the investigational intervention or any of its excipients, clinically significant multiple or severe drug allergies, intolerance to topical corticosteroids, or history of severe post-treatment hypersensitivity reactions, including, but not limited to, erythema multiforme major, linear immunoglobulin A (IgA) dermatosis, toxic epidermal necrolysis, or exfoliative dermatitis.

Diagnostic assessments or abnormal laboratory values

- [43] Have any of the following specific abnormalities on screening laboratory tests:
- alanine aminotransferase (ALT) or aspartate aminotransferase (AST) >2 times upper limit of normal (ULN)
 - total bilirubin level (TBL) ≥ 1.5 times ULN
 - hemoglobin <8.5 g/dL (<85.0 g/L)
 - total white blood cell count (WBC) <2500 cells/ μ L (<2.50 $\times 10^3$ / μ L or <2.50 GI/L)
 - eosinophilia (absolute eosinophil count >3000 cells/ μ L (>3.0 $\times 10^3$ / μ L or >3.0 GI/L)
 - neutropenia – absolute neutrophil count (ANC) <1000 cells/ μ L (<1.00 $\times 10^3$ / μ L or <1.00 GI/L)
 - lymphopenia – absolute lymphocyte count (ALC) <500 cells / μ L (<0.50 $\times 10^3$ / μ L or <0.50 GI/L)
 - thrombocytopenia – platelets <50,000 cells/ μ L (<50 $\times 10^3$ / μ L or <50 GI/L)
 - estimated glomerular filtration rate (eGFR) (Modification of Diet in Renal Disease [MDRD]) <50 mL/min/1.73 m² (FDA 2010).

Note: For repeat testing of screening laboratory tests, see Section 5.4.1.

- [44] Have known hypogammaglobulinemia or a screening immunoglobulin G (IgG) level <565 mg/dL (<5.65 g/L).

- [45] Have other abnormal laboratory values at screening that, in the opinion of the investigator, indicate unacceptable risk for the participant's safety in the study.
- [46] Have screening electrocardiogram (ECG) abnormalities that, in the opinion of the investigator, are clinically significant and indicate an unacceptable risk for the participant's safety in the study.

Previous or concurrent clinical study experience

- [47] Have previously been randomized in this study or have received LY3471851 in any previous study.
- [48] Are currently enrolled in any other clinical study involving an investigational product or any other type of medical research judged not to be scientifically or medically compatible with this study.

Other exclusions

- [49] Are largely or wholly incapacitated, permitting little or no self-care, such as being bedridden or confined to wheelchair.
- [50] Have donated more than a single unit of blood within 4 weeks before randomization (Visit 2) or intend to donate blood during the course of the study.
- [51] Have a history of chronic alcohol abuse, intravenous (IV) drug abuse, or other illicit drug abuse within 1 year before screening.

Note: Marijuana is considered an illicit drug for the purposes of this study, regardless of local laws. Cannabidiol (CBD) products may be used during the study if they are derived exclusively from hemp. Participants who use hemp-based CBD products must be on a stable dose for at least 10 days prior to randomization, and participants must remain on that stable dose during the study.

- [52] Are unable or unwilling to make themselves available for the required number of study visits or unwilling to follow the restrictions and procedures of the study.
- [53] Are women who intend to become pregnant or breastfeed at any time in the study.
- [54] Are investigative site personnel directly affiliated with this study and/or their immediate families. Immediate family is defined as a spouse, parent, child, or sibling, whether biological or legally adopted.
- [55] Are employees of Eli Lilly and Company (Lilly) or are employees of a third-party organization involved in the study, which requires exclusion of their employees.

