Note: A psychiatrist or appropriately trained professional may assist in the decision to discontinue the participant.

- The investigator, after consultation with the sponsor's designated medical monitor, determines that a systemic hypersensitivity reaction has occurred and is related to study drug administration.
- The participant has any of the following results on 2 consecutive samples taken at least 48 hours, but no more than 1 week, apart.
 - Total WBC <1000 cells/ μ L
 - ANC <500 cells/ μ L
 - ALC <200 cells/ μ L
 - Hemoglobin <6.5 g/dL
- The participant develops CRS. In consultation with the Lilly medical monitor, if an adverse event is deemed possibly or probably due to CRS based on the details and severity of clinical signs and symptoms, time course of symptom onset relative to study drug administration, and if possible, a cytokine panel from a blood sample obtained at the time of the event, the participant will be discontinued from study treatment, and will continue safety follow-up.
- The participant develops hypereosinophilia.
 - Participants with absolute eosinophil counts >1500 cells/ μ L and signs and/or symptoms of target organ involvement that is not consistent with lupus and/or with the

participant's lupus and medical history will be discontinued from study drug in consultation with the medical monitor. Participants will undergo appropriate medical evaluation, which should take into account the participant's known lupus and past medical history according to the participant's history and medical records, including previous imaging, biopsies and laboratory findings. Evaluation of target organ involvement will involve additional diagnostic tests as appropriate, including laboratory tests, imaging (for example, echocardiogram, CXR, computed tomography [CT] scan) and biopsies. New onset cardiac, pulmonary, and skin findings in the setting of peripheral eosinophilia will be considered as target organ involvement, unless attributable to other causes.

- Asymptomatic participants with an absolute eosinophil count >5000 cells/ μ L should have a repeat measurement to confirm the count. If the count is confirmed, the participant will be permanently discontinued from study drug and undergo appropriate medical evaluation.
- The participant has an adverse event or a SAE or a clinically significant change in a laboratory value that, in the opinion of the investigator, merits the discontinuation of the study drug and appropriate measures being taken.

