Hepatic event or liver test abnormality

- Participants who are discontinued from study drug because of a hepatic event or liver test abnormality should have additional hepatic safety data collected via the hepatic eCRF packet. Discontinuation of study drug because of abnormal liver tests should be considered by the investigator when a participant meets one of the following conditions after consultation with the sponsor's designated medical monitor (see Section 8.2.9).
 - ALT or AST >8 times ULN
 - ALT or AST >5 times ULN sustained for more than 2 weeks
 - ALT or AST >3 times ULN and TBL >2 times ULN or international normalized ratio (INR) >1.5
 - ALT or AST >3 times ULN with the appearance of fatigue, nausea, vomiting, right upper-quadrant pain or tenderness, fever, rash, and/or eosinophilia ($>5\%$)
 - alkaline phosphatase (ALP) >3 times ULN
 - ALP >2.5 times ULN and TBL >2 times ULN, or
 - ALP >2.5 times ULN with the appearance of fatigue, nausea, vomiting, right upper quadrant pain or tenderness, fever, rash, and/or eosinophilia ($>5\%$).

Other reasons

- Unblinding: If an investigator, blinded site personnel who are performing assessments, or participant is unblinded to a participant's treatment assignment, the participant must be discontinued from the study drug and continue to post-treatment follow-up. In cases where there are ethical reasons to have the participant continue on study drug, the investigator must obtain specific approval from the sponsor's designated medical monitor for the participant to continue.

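### Criterion [43] has no numeric ALP limit, and above a baseline of 1.5 × ULN the timed ALP repeat in 8.2.9 comes after the 7.1.1 level for considering discontinuation

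*Protocol*

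**What the plan says.** **Entry.** Protocol 5.2, criterion [43], begins "Have any of the following specific abnormalities on screening laboratory tests" and then lists its tests. The hepatic entries are ALT/AST >2 × ULN and total bilirubin (TBL) ≥1.5 × ULN. The rest are hemoglobin, WBC, eosinophils, neutrophils, lymphocytes, platelets and eGFR. ALP is not on the list, and no other criterion gives an ALP number. Two criteria work by judgment: [45], "Have other abnormal laboratory values at screening that, in the opinion of the investigator, indicate unacceptable risk", and [37], which covers hepatic and other disorders that "could constitute an unacceptable risk to the participant when taking an investigational product". An eligibility review committee confirms entry before randomization (Protocol 5 and 10.1.5).

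**Stopping.** Protocol 7.1.1 says that discontinuation for abnormal liver tests "should be considered by the investigator when a participant meets one of the following conditions after consultation with the" medical monitor. One listed condition is "alkaline phosphatase (ALP) >3 times ULN", with no adjustment for baseline.

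**Monitoring.** Protocol 8.2.9 has two tables, one for a repeat within 48 to 72 hours and one for comprehensive evaluation. With baseline ALP below 1.5 × ULN, the ALP triggers are 2 × ULN and 3 × ULN respectively. With baseline ALP at or above 1.5 × ULN, both triggers are twice baseline. Protocol 8.2.9.1 uses the same twice-baseline multiple, on consecutive tests, for the hepatic case report form.

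**Risk.** Protocol 2.3 cites nonclinical biliary hyperplasia and warns of possible cholestasis.

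**The concern.** ALP is a liver test directly relevant to the biliary risk that the protocol names, yet it has no numeric gate at entry. Two things follow.

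- A patient with an isolated screening ALP above 3 × ULN meets no numeric exclusion. If randomized with ALP unchanged, that patient would start treatment at a level where 7.1.1 asks the investigator to consider stopping.
- The usual order is a timed repeat first and then, if the value keeps rising, a discussion about stopping. For participants who start above 1.5 × ULN this order reverses.

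At stake is prompt confirmation of a rising ALP in the few participants who begin with a raised one. This matters most after Week 12, when scheduled chemistry is 28 days apart and the dosing visits at Weeks 14, 18 and 22 have none (Protocol 1.3). No efficacy endpoint or error rate is involved.

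**Working it through.** The plan states no figure of its own on this point, so the check compares thresholds.

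**Inputs**
- 7.1.1 isolated ALP condition: >3 × ULN.
- 8.2.9, baseline <1.5 × ULN: repeat at ≥2 × ULN, comprehensive evaluation at ≥3 × ULN.
- 8.2.9, baseline ≥1.5 × ULN: both at ≥2 × baseline.
- Baseline is taken as the most recent pre-dose value, as 9.4.1 defines it for the analyses. Section 8.2.9 gives no definition of its own.

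**Formula.** Let baseline ALP be b × ULN. For b ≥ 1.5 the trigger is 2b. It exceeds 3 when 2b > 3, that is, when b > 1.5.

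| Baseline b (× ULN) | Repeat trigger | Comprehensive trigger | Repeat trigger minus 3.0 |
|---|---|---|---|
| 1.4 | 2.0 | 3.0 | −1.0 |
| 1.5 | 3.0 | 3.0 | 0 |
| 1.6 | 3.2 | 3.2 | +0.2 |
| 2.0 | 4.0 | 4.0 | +1.0 |
| 2.4 | 4.8 | 4.8 | +1.8 |
| 3.1 | 6.2 | 6.2 | +3.2 |

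At b = 1.5 the two levels coincide. Above it, the 8.2.9 ALP trigger always comes after the 7.1.1 level. A participant with baseline 1.6 and an isolated ALP of 3.1 × ULN meets the 7.1.1 condition while both 8.2.9 ALP triggers are still at 3.2. This assumes that the separate ALT/AST and TBL triggers have not fired.

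**Chemistry schedule (Protocol 1.3).** Weeks 0, 1, 2, 4, 6, 8, 10, 12, 16, 20 and 24: intervals of 7 to 14 days to Week 12, then 28 days.

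**Effect of the proposed change.** With an entry limit of ≥1.5 × ULN, a participant whose ALP stays below 1.5 up to the first dose has a repeat trigger of 2.0, which is 1.0 × ULN below the 7.1.1 level. For anyone whose last pre-dose value is still ≥1.5, min(2b, 3.0) = 3.0, so the trigger becomes level with 7.1.1 and no longer lies above it.

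**Possible reach (assumption only).** Protocol 9.2 gives 70 per group, so 70 × 4 = 280. If 0%, 0.5%, 1% or 2% had baseline ALP ≥1.5 × ULN, that would be 0, 1.4, 2.8 or 5.6 people. Only those with a further isolated rise would be exposed to the gap.

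**The case against.** The case for leaving the plan alone has real force.

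- **Entry is not unguarded.** [45] exists for unlisted laboratory abnormalities, [37] covers hepatic disorders, and a committee confirms eligibility. A reader might infer that a patient with ALP above 3 × ULN would enter unchecked. The documents do not support that. What is missing is a number, not a check, although the committee's stated emphasis is SLE disease activity.
- **7.1.1 governs participants on study drug and is discretionary.** A reader might infer that such a patient would have to be stopped at once. The text asks only that stopping be considered, after consultation.
- **The stronger action comes first.** Above 3 × ULN the medical monitor is already involved, which is more than a repeat test. Investigator review with repeat of clinically significant values (8.2.5), withholding (7.1.2.2), blinded sponsor review at least quarterly (8.2) and unblinded committee review (10.1.5) also apply. A reader might infer that monitoring lapses in the gap. It does not. However, none of these sets an ALP level with a timed repeat.
- **A baseline-relative rule is reasonable.** It helps separate a drug effect from a stable pre-existing elevation. That justifies a relative trigger, but not one with no upper bound.

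It is also tempting to call ALP the sole anomaly, because other tests have an entry limit stricter than the stopping level, such as "hemoglobin <8.5 g/dL (<85.0 g/L" g/L) at entry against "Hemoglobin <6.5 g/dL" on study. The comparison is not like for like. The blood-count criteria need two consecutive samples. The rule for "Asymptomatic participants with an absolute eosinophil count >5000" cells/µL requires discontinuation once the count is confirmed. The liver list only asks for consideration. ALT also shows a similar reversal: a baseline of 1.6 × ULN gives a trigger of 3.2, above the 7.1.1 condition of >3 × ULN with symptoms. Likewise, [43] admits eosinophils up to 3000 cells/µL, although 7.1.1 acts above 1500 when target organs are involved.

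**Conclusion.** The point holds as an optional patient-safety improvement. [43] has no numeric ALP limit, so a raised screening ALP is excluded only by judgment. For every baseline above 1.5 × ULN, the timed repeat in 8.2.9 falls after the 7.1.1 level for considering discontinuation: by 0.2 × ULN from a baseline of 1.6 and by 1.0 × ULN from 2.0. The loss is the automatic early repeat, not the consultation or general monitoring. The number of participants concerned cannot be derived from the documents and may be zero. The conclusion rests on reading baseline in 8.2.9 as the last pre-dose value, and on an ALP rise that trips no ALT/AST or TBL trigger.

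**What to change.** **(a)** Add ALP ≥1.5 × ULN to [43]. This matches the TBL limit and the baseline split in 8.2.9, and it removes the reversal at entry.

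**(b)** Visit 1 may precede randomization by 3 to 35 days, so a few participants may still have a last pre-dose ALP of 1.5 × ULN or more. For them, change the ALP row in both 8.2.9 tables to ≥2 × baseline or ≥3 × ULN, whichever is lower. Make the same change in the matching 8.2.9.1 row, keeping its requirement for consecutive tests, so that the sections agree.

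A cap lower than 3 × ULN is not advised. At 2.5 × ULN, a participant starting at 2.4 would trigger a repeat on a 4% rise (2.5/2.4 = 1.04). A confirmation step at Visit 2 is not advised either, because chemistry and first dosing share that visit and the result would probably arrive after the dose. One limit remains: a 3 × ULN cap gives no lead time against the separate 7.1.1 condition of ALP >2.5 × ULN with symptoms.

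**Cost.** One line in [43], one row in each 8.2.9 table and one in 8.2.9.1. ALP is already in the chemistry panel drawn at Visits 1 and 2. The downside is an unquantified number of extra screen failures, including ALP raised for non-hepatic reasons, plus a few repeat tests. The single chemistry retest allowed in 5.4.1 limits the screen failures.
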